**Causality criteria:**

*Related to the IMP:* The temporal relationship of the AE/SAE onset to the administration of the IMP makes a causal relationship possible, and other drugs, therapeutic intervention or underlying conditions do not provide a sufficient explanation for the AE/SAE.

*Not related to the IMP:* The temporal relationship of the AE/SAE onset to the administration of the IMP makes a causal relationship unlikely, or other drugs, therapeutic interventions or underlying conditions provide a sufficient explanation for the AE/SAE.

**Severity criteria:**

*Mild:* Discomfort noticed, but it does not affect normal activity.

*Moderate:* Discomfort sufficient to reduce or affect normal daily activity.

*Severe:* Incapacitating with inability to perform normal daily activity.

**Clinical safety assessments** are detailed in section “4.2. Clinical follow up visits in Aurora hospital.” Additionally pregnancy test for females of child-bearing potential is done during the first visit in Obesity Research Unit.

Possible unexpected adverse events due to study regimens are covered by the **Pharmaceutical Injury Insurance (Lääkevahinkovakuutus)**.

All subjects are insured by the **patient insurance of Helsinki University Hospital**.

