## 5.2 Raltegravir

Raltegravir (trade name Isentress®) is an HIV medicine that is used in combination with other HIV medicines to treat adults and children who are infected with human immunodeficiency virus (HIV-1). It is developed and manufactured by Merck Sharp & Dohme Corp (MSD). The European Commission granted a conditional marketing authorisation valid throughout the European Union for Isentress on 20th December 2007. This was switched to a full marketing authorisation on 14th July 2009. A new formulation of Isentress 600mg coated tablets was granted a marketing authorisation by European Comission on 18th July 2017. The recommended daily dose for the new formulation is 1200 mg (two 600 mg tablets) once daily. In this study, we plan to use the once daily formulation of raltegravir. This study drug is provided by Merck Sharp & Dohme Corp.

Raltegravir is one of the best tolerated HIV-medicines. The most common reported adverse effects with Isentress (seen in between 1 and 10 patients in 100) are abnormal dreams, nightmares, insomnia, depression, abnormal behavior, dizziness, headache, psychomotor hyperactivity, vertigo, decreased appetite, abdominal distension, abdominal pain, diarrhea, flatulence, nausea, vomiting, dyspepsia, rash, asthenia, fatigue, pyrexia, atypical lymphocytes, and increased blood levels of some enzymes (alanine aminotransferase, aspartate aminotransferase, lipase and pancreatic amylase) and triglycerides. For more details of the study drug, see SmPC of Isentress attached.

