## 5.3. Adverse events assessment

**An AE** is any untoward medical occurrence in a study subject administered a pharmaceutical product and which does not necessarily have a causal relationship with this treatment. An AE can therefore be any unfavourable and unintended sign (including an abnormal laboratory finding), symptom, or disease temporally associated with the use of an investigational medicinal product (IMP), whether or not related to the IMP. The definition also covers medication errors and uses outside what is foreseen in the protocol, including misuse and abuse of the product.

Thus, an AE may be an appearance or worsening of any undesirable sign or symptom, any worsening of the current medical conditions or onset of a new disease, compared with the previous observations or a clinically significant adverse change in a laboratory variable or other diagnostic finding.

**A serious adverse event (SAE)** is any untoward medical occurrence that

- results in death
- is life-threatening
- requires inpatient hospitalization or prolongation of existing hospitalization
- results in persistent or significant disability/incapacity
- is a congenital anomaly/ birth defect, or
- is an important medical event jeopardizing the patient or requiring intervention to prevent serious outcome (examples of such are intensive treatment in an emergency room, convulsions that do not result in hospitalization, etc.)

Any case of pregnancy during a clinical study will be reported by the investigator in the same way as an SAE.

**Other significant AEs** are AEs (other than those meeting the definition of serious) that are of clinical importance and lead to:

- a diagnostic or therapeutic intervention
- discontinuation of the IMP

- significant additional concomitant treatment, or
- marked hematological and other laboratory abnormalities

**Suspected Unexpected Serious Adverse Reaction** or “**SUSAR**” shall mean any Serious Adverse Event, the nature, severity or frequency of which is not consistent with information in the most current Summary of Product Characteristics (SmPC) or Package Insert.

All AEs must be elicited, documented and reported by the investigator. The investigator will assess and record the causality and severity of the AEs due to IMP (see criteria for causality and severity below). SAEs and other significant AEs should be followed up until resolved or until the event is considered a chronic or stable outcome, or both.

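### The AE severity scale has no usable grade for a symptom-free laboratory abnormality, although the protocol counts such findings as AEs

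*Combined protocol and SAP*

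**What the plan says.** Section 5.3 (Adverse events assessment) defines an AE to include any "unfavourable and unintended sign (including an abnormal laboratory finding), symptom, or disease". It adds that an AE may be "a clinically significant adverse change in a laboratory variable or other diagnostic finding". Neither phrase requires the subject to feel anything.

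The same section states: "The investigator will assess and record the causality and severity of the AEs due to IMP". It then points to criteria given below it. Those criteria, under Severity criteria, have three steps:
- Mild: "Discomfort noticed, but it does not affect normal activity".
- Moderate: "Discomfort sufficient to reduce or affect normal daily activity".
- Severe: the subject is incapacitated and cannot carry on with daily activity.

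Section 5.3 also has a class of other significant AEs, which are followed until they resolve or become stable. One of its four triggers is "marked hematological and other laboratory abnormalities". No value is given that makes an abnormality marked, and the class carries no severity grade. No numeric laboratory limits or other toxicity scale appear in the document.

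Section 5.2 lists among the common effects of raltegravir "increased blood levels of some enzymes (alanine aminotransferase, aspartate aminotransferase, lipase and pancreatic amylase) and triglycerides". Secondary objective 8 in section 2 is the collection of safety and tolerability data on the switch.

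**The concern.** The plan makes a class of event reportable, asks for its severity, and supplies a scale that cannot be applied to it. Much of the scheduled safety information belongs to that class. Table 1 in section 4.2 has laboratory draws at all four contacts, and section 4 describes the draws at weeks 2 and 8 as safety tests.

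The quality of the severity data for objective 8 is at stake. With no written basis for grading a symptom-free value, an investigator must leave the grade blank, default to mild, or use a private rule. The trial is open-label, so a private rule could differ between investigators or between arms. Subjects are selected for metabolic risk or hepatosteatosis, and the exclusion criteria set no limit on liver enzymes. Some may therefore start with raised values, and the scale does not refer to baseline.

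**Working it through.** The plan has no figure to reproduce here. The check sets the definitions side by side and then looks at which measurements they apply to.

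**Step 1. Is a symptom-free laboratory abnormality an AE?** Yes. Both definitions in section 5.3 cover it without a symptom.

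**Step 2. Must it be graded?** Yes if it is attributed to the study drug. For other AEs the wording is unclear, because the sentence on severity is qualified as concerning events due to the IMP. ALT and AST rises are among the listed effects of raltegravir, so at least some laboratory AEs fall within the narrower reading.

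**Step 3. Which grade applies?** Take two illustrative ALT values in a subject who feels well. The multiples are assumed and are not in the protocol.

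| Criterion | ALT 2 × upper limit | ALT 15 × upper limit |
|---|---|---|
| Mild: discomfort is noticed | not met | not met |
| Moderate: discomfort affects daily activity | not met | not met |
| Severe: incapacitated | not met | not met |

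The columns are identical. Any other pair of values gives the same result, because no criterion refers to a value. If mild is read loosely as the floor of the scale, both events are mild. If it is read strictly, neither has a grade. On either reading the scale cannot rank them.

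**Step 4. Does another rule supply the ranking?** The class of other significant AEs separates marked from unmarked abnormalities. It gives no limit and assigns no severity, so it does not.

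**Step 5. Which scheduled measurements are concerned?** From Table 1, for the four measures most relevant to safety:

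| Measure | Day 1 | Week 2 | Week 8 | Week 24 | After day 1 |
|---|---|---|---|---|---|
| ALT | yes | yes | yes | yes | 3 |
| AST | yes | no | yes | yes | 2 |
| Creatinine | yes | yes | yes | yes | 3 |
| Blood count | yes | yes | yes | yes | 3 |

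Each subject has 3 + 2 + 3 + 3 = 11 scheduled results after day 1 on these measures, and each measure has a day 1 value. A value-based grade and a shift from baseline can therefore be derived without a new sample. The 11 is a count of scheduled results. It does not estimate how many will be abnormal, and the documents give no basis for that.

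**The case against.** The strongest reply is that little depends on the severity label, and much of that reply stands.

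- **Follow-up.** A reader might infer that follow-up of a large enzyme rise depends only on what an investigator takes *marked* to mean. The documents do not support this. Section 5.3 has three other triggers: a diagnostic or therapeutic intervention, stopping the IMP, and significant additional concomitant treatment. A rise that led to any of these would be followed whatever its grade.
- **Serious events.** Seriousness is judged separately from severity, and the SAE definition covers important medical events. Expedited reporting is untouched.
- **Hidden differences.** A reader might infer that a difference between arms in liver enzymes would be lost. It would not. The results are recorded, and section 6 commits to analysing all variables and testing differences between groups.
- **Published safety table.** A reader might predict an AE table with no moderate or severe laboratory events in either arm. The plan contains no such table. Section 6 does not mention one, and the publication plan names objectives 1 to 3 for the main manuscript. The effect is on the recorded grades and on any summary later built from them.
- **Scope.** Severity is tied on its face to events due to the IMP, so it is too broad to say that every AE must be graded. This narrows the point without removing it, and it leaves grading in the control arm unclear.
- **Size by counting.** The share of laboratory items among the effects listed in section 5.2 does not measure the problem. It counts effect names and says nothing about how often they occur. Lipase and pancreatic amylase are not named in any scheduled panel.

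It can also be said that investigators will use judgement. The written criteria give that judgement nothing to work from when there are no symptoms.

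**Conclusion.** The point holds in a limited form. A symptom-free laboratory AE of any size cannot be graded moderate or severe under the protocol, and strictly it has no grade. It goes too far to say that the scale produces a wrong grade; the text supports only that no valid grade above mild exists. Severity data for objective 8 therefore cannot distinguish small from large changes in ALT, AST, creatinine or blood count.

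The consequence is confined to severity grading within one secondary objective. The primary endpoint, sample size, SAE reporting, follow-up triggers and raw values are not affected. No numerical size can be attached, because the documents do not give the expected frequency of symptom-free laboratory AEs.

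The conclusion assumes that the three-step scale is the only severity rule in use. It does not depend on whether severity is recorded for all AEs or only for those attributed to raltegravir.

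**What to change.** 1. Keep the three-step scale for symptomatic AEs.
2. Grade laboratory AEs by value on one named published numeric toxicity table. State how a baseline that is already raised is taken into account, and name the blood-count components to be graded.
3. Apply the table identically in both arms, and reword the sentence on severity so that it is clear whether control-arm events are graded.
4. State which grade on that table counts as marked when classifying other significant AEs in section 5.3.
5. Report shift from the day 1 value by arm for ALT, AST, creatinine and blood count. AST has no week 2 result in Table 1, so its shifts would be at weeks 8 and 24.

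The cost is protocol wording and a derivation from results already collected, with no added visit or sample. One downside is that more laboratory events may be graded moderate or severe than now. The change is best made before grading starts, so that laboratory AEs need not be re-graded with treatment known. It sets no treatment or stopping rule.

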## 6. Data analysis

The data will be analyzed by the investigators and the study group.

All variables of the data will be analyzed after the last subject's last visit, when the data have been declared complete.

The data will be analyzed using IBM SPSS Statistics v. 22. The differences between the groups will be analyzed by using chi-square, Fisher's exact, Mann-Whitney U test and others, as appropriate.

As there are no earlier ART-switch studies using H-Magnetic resonance spectroscopy for the quantification of liver fat, the calculation of the study power is an estimate. In the STERAL study evaluating the effect of switching from efavirenz (EFV) to RAL vs. continuing Efv-based ART, a statistically significant difference in the liver fat content using CAP (controlled attenuated parameter) was shown with a study sample of 19 +18 subjects after 48 weeks (7,3% decrease in the RAL vs. 11,0% increase in the Efv arm, p = 0,019) (11).

The power of this study is calculated with the assumption of liver fat being 4.4-5.0% in this study group at baseline. This estimation is based on our previous results published in 2002, when the median liver fat was 8% with lipodystrophic patients and 3% with non-lipodystrophic patients (17). Hadigan et al reported liver fat content being >5% in 42% of HIV positive subjects (18). As the liver fat content correlates with visceral fat mass, studying overweight or obese patients with at least one metabolic syndrome component includes patients at high risk for elevated liver fat content.

In the power calculation, we have used a coefficient of variation (CV) of H-Magnetic resonance spectroscopy being 11% (17). To detect a 9% difference between study arms with 80% power, a minimum sample size of 25 + 25 subjects with a 10% drop-out rate is needed.

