## 2. List of study objectives

Primary objective is:

1. Baseline to 24-week Change in Liver Fat (measured by proton magnetic resonance spectroscopy,  $\Delta \%$ )

Secondary objectives are:

1. Baseline to 24-week Change in Body Composition including subcutaneous and visceral adipose tissue volume (measured by magnetic resonance imaging), total body fat and lean tissue mass (measured by Bioelectrical Impedance Analysis)
2. Baseline to 24-week Change in Liver Stiffness measured by transient elastography (Fibroscan ®)
3. Baseline to 24-week Change in Glucose Metabolism including fasting glucose, insulin, 2-h oral glucose tolerance test
4. Baseline to 24-week Change in Lipid Profile (LDL and HDL cholesterol, Triglyceride)
5. Baseline to 24-week Change in Metabolic and Inflammatory Biomarkers (e.g. high-sensitivity C-reactive protein (hsCRP), adiponectin, etc)
6. To collect subcutaneous adipose tissue samples at baseline and 24 weeks for future gene expression studies
7. To collect stool and saliva samples at baseline and 24 weeks for future microbiome studies
8. To collect safety and tolerability data related to the switch to raltegravir
9. Determination of the fatty liver adipose allele (B-PNPLA3)
10. Determination of basal metabolic rate by indirect calorimetry at screening and at the end of study

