##### Intrahepatic fat content (1H Magnetic resonance spectroscopy, MRS)

Single voxel (25x25x25 mm^3) proton spectra from the liver will be acquired using 16 excitations, a body matrix surface coil and a 1.5-tesla magnetic resonance device (Avantofit).

Siemens, Erlangen, Germany). A Point resolved spectroscopy (PRESS) single voxel technique will be applied, with an echo time of 30 ms. Respiratory motion will be triggered using a navigator belt so that repetition time will be kept  $> 3000$  ms. Intensities of water signal ( $S_{\text{water}}$ ) ppm and methylene signal ( $S_{\text{fat}}$ ) representing intracellular triglyceride in the liver, resonating at 4.8 and 1.4 ppm, respectively, will be determined. Effects of T2 relaxation will be corrected for water and fat intensities and hepatic fat percentage will be calculated by dividing  $S_{\text{fat}}$  by the sum of  $S_{\text{fat}}$  and  $S_{\text{water}}$ . Signal ratios will be further converted to mass fractions as previously described (15). This measurement of percent hepatic fat by proton spectroscopy has been validated against the lipid content of liver biopsies in humans (16). MRI and MRS methods involve no ionizing radiation exposure.

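### Scale and test for the primary endpoint are left open: fix one scale and one baseline-adjusted analysis, reported with an estimate and 95% CI

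*Combined protocol and SAP*

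**What the plan says.** - Primary endpoint (protocol section 2): "Baseline to 24-week Change in Liver Fat (measured by proton magnetic resonance spectroscopy", with the unit Δ%. The text does not say whether this is a difference in percentage points or a change relative to baseline.
- Measurement (section 4.3, intrahepatic fat content): "hepatic fat percentage will be calculated by dividing" the fat signal by the sum of fat and water signals, then converting to a mass fraction. The quantity whose change is taken is therefore already a percentage.
- Tests (section 6): "The differences between the groups will be analyzed by using chi-square, Fisher's exact, Mann-Whitney U test and others, as appropriate". The list covers all variables. Its only named test suited to a continuous outcome is the Mann-Whitney U, which does not adjust for baseline. No transformation, covariate, effect measure, confidence interval or alpha is given.
- Sizing (section 6): "The power of this study is calculated with the assumption of liver fat being 4.4-5.0% in this study group at baseline"; "we have used a coefficient of variation (CV) of" spectroscopy of 11%. The target is worded "To detect a 9% difference between study arms with 80% power"; for that target the plan concludes that "a minimum sample size of 25 + 25 subjects with a 10% drop-out rate is needed".
- Conduct: section 4 describes an open-label design. Section 6 has the investigators and study group analyse the data after the last visit, once the data are declared complete. Section 3 stratifies randomisation by age, sex and regimen (PI or efavirenz), but section 6 does not use these factors.

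**The concern.** Two choices that can change the primary result are left until the data are complete, in the hands of people who know the allocation: the scale of the change, and the test. The scales are not interchangeable when baseline liver fat varies. Section 6 cites earlier medians of 3% and 8%; a 9% relative change is 0.27 points at the first and 0.72 points at the second, so a points analysis and a relative analysis weight patients differently. At stake are control of the false-positive rate and the ability to interpret the result: a p-value from an unspecified test gives no size of effect to set against the difference used for sizing. Baseline liver fat is measured in every subject but has no planned role in the analysis beyond forming the change.

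**Working it through.** **Inputs.** From the documents: difference 9%, CV 11%, power 80%, drop-out 10%, baseline 4.4-5.0% (midpoint 4.7%), 1:1 allocation, 45 subjects in section 3. About 41 are evaluable (45 × 0.9 = 40.5), taken as 21 + 20. Assumed, because not in the documents: two-sided alpha 0.05; lognormal baseline with median 4.7% and log-SD s = 0.6-1.0; correlation r between log baseline and log week-24 value.

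**1. The plan's own figure.** n per arm = 2(1.960 + 0.842)² × (SD/δ)².
- Log scale: δ = -ln(0.91) = 0.0943, SD = √ln(1 + 0.11²) = 0.1097. This gives 21.2, so 22; 22/0.9 = 24.4, so 25 per arm. It matches the stated 25 + 25.
- Percent scale, δ = 9, SD = 11: 24 by this formula, or 24.4 (so 25) by t-test, before drop-out; 27 or 28 after it.
- Nine percentage points would exceed the whole assumed baseline of 4.4-5.0%, so that reading fails.
- Both figures converted to points at 4.7%: δ = 0.09 × 4.7 = 0.42, SD = 0.11 × 4.7 = 0.52. The ratio is still 9/11, so n is the same as on the percent scale.

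The relative reading is the more natural one, but the arithmetic does not prove it.

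**2. False positives when the choice is open.** No true effect, 21 + 20, s = 0.6-1.0, SD of log change 0.11 or 0.156 or r = 0.9, 0.8, 0.6; 10,000 simulated trials per setting:

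| Reported result | Rate of p < 0.05 |
|---|---|
| Any single test fixed in advance | 3.8-5.4% |
| Better of Mann-Whitney on points or on relative change | 5.9-6.9% |
| Best of four (Mann-Whitney or t-test, points or log ratio) | 7.8-9.0% |

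The inflation barely depends on the SD or r, so it does not rest on 11% being the right SD.

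**3. Does one scale have more power?** That depends on how the data arise.
- Multiplicative effect and error (9% reduction, SD of log change 0.11): Mann-Whitney on points 60-65%, Mann-Whitney on relative change 73-74%, log model with baseline 75-76%.
- Additive effect (0.42 points) and error (SD 0.52 points), 1.0% floor: Mann-Whitney on points about 65-70%, log model with baseline about 49-60%. The order reverses.

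**4. Value of adjusting for baseline.** On the log scale the variance of the adjusted comparison is s²(1 - r²), against 2s²(1 - r) for the change: a ratio of (1 + r)/2, which is 0.80 at r = 0.6 and 0.90 at r = 0.8. Power for s = 0.6 / 0.8 / 1.0:

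| Setting | t-test on log ratio | Log model with baseline |
|---|---|---|
| 40% reduction (assumed), r = 0.6 | 84.0 / 60.4 / 42.4% | 90.8 / 68.8 / 50.4% |
| 40% reduction (assumed), r = 0.8 | 98.6 / 88.4 / 71.8% | 99.0 / 90.8 / 75.2% |
| 9% reduction, SD of log change 0.11 (r about 0.98-0.99) | 76.1 / 76.0 / 76.5% | 75.3 / 75.4 / 75.6% |

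Adjustment gains about 7-8 points at r = 0.6 and 0-3 at r = 0.8, and costs under 1 point at very high r. Adding balanced stratification factors changed power by at most 0.6 points (for example 75.4% to 74.8%).

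**5. Near-zero values.** Eligibility sets no minimum liver fat by spectroscopy, and logs are unstable near zero. In the 9%, SD 0.11 setting, flooring values at 1.0% takes the log model from 75.3 / 75.4 / 75.6% to 75.6 / 74.5 / 72.9%: a cost of up to 2.7 points.

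**The case against.** The strongest reply is that the real gap is narrow and that a preference for a log model goes beyond it. Several parts of this stand.

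- A reader might infer that the trial was certainly sized on a relative scale, so that a points analysis would test a different effect. The documents do not support that: step 1 gives the same n after conversion to points, and stating a baseline level for the power calculation fits such a conversion too.
- A reader might quote the power gap in step 3 as a property of this trial. It is not. It comes from assuming multiplicative data, and the order reverses under additive data. With an assumed fixed scan error of 0.2 points the log model has no real advantage either: 45-57%, depending on the floor, against 49-55% for Mann-Whitney on points.
- A reader might want the interval judged against a ratio of 0.91. The plan gives its 9% neither a direction nor the status of a margin. At r = 0.8 and s = 0.8 the 95% CI half-width would be about 36%, so the interval could rarely separate 0.91 from 1.
- The 8-9% counts t-tests, which section 6 never names, and both rates assume that the most favourable result is always reported. They show what the wording permits; they do not predict conduct.
- The wording about other tests does not exclude adjustment, and the synopsis listed as an attachment is not available and might define the endpoint.

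None of this closes the gap. The documents at hand still leave the unit undefined and no test assigned, and the openness that would permit an adjusted analysis also permits choosing after the results are seen.

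**Conclusion.** The point holds in limited form. The primary endpoint lacks a defined scale, an assigned test, a planned use of baseline as a covariate, and an estimate with CI, in an open-label trial analysed by its own investigators. The cost is a false-positive rate of about 6-7% if the choice is only between Mann-Whitney on two scales, and 8-9% if t-tests are also allowed. Those rates rest on assumed lognormal liver fat and best-result reporting, but hardly on the SD or the correlation. A relative scale is the more natural reading of the plan's figures, as an inference only. Neither scale can be called more powerful from the documents. Two matters are separate and not relied on here: the use of a method CV as the outcome SD, and 45 subjects in section 3 against 25 + 25 in section 6.

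**What to change.** Before any week-24 spectrum is read, amend sections 2 and 6 to:

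1. State whether the primary endpoint is relative change or change in percentage points.
2. Name one primary analysis, adjusted for baseline liver fat and for age, sex and regimen, with a stated alpha, reported as an estimate with 95% CI. Suggested: a linear model of log week-24 liver fat on arm, log baseline liver fat and the stratification factors, reported as a ratio of geometric means. If the team intends points, the matching model on the untransformed scale serves the same purpose.
3. If logs are used, set a rule for near-zero values from the baseline spectra. The documents give no quantification limit, so any floor (1.0% was tried above) is an assumption to confirm.
4. Keep Mann-Whitney on the same scale, with a Hodges-Lehmann estimate and CI, as a sensitivity analysis.

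The cost is a few sentences and no new data. Statistically it takes a few degrees of freedom: about 1 point of power or less when baseline correlation is high, against a gain of up to about 8 points at r = 0.6 under an assumed 40% reduction. A 1.0% floor can cost up to about 3 points. If effect and error are in fact additive, the log model has lower power than a points analysis; the team should accept that risk knowingly when it fixes the scale.

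### The 80% power for a 9% difference rests on the 11% CV of the MRS method; no SD of the 24-week change in liver fat is given

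*Combined protocol and SAP*

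**What the plan says.** Section 2 defines the primary objective as "Baseline to 24-week Change in Liver Fat (measured by proton magnetic resonance spectroscopy", expressed as a delta in percent.

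Section 6 justifies the sample size for it. Baseline liver fat enters as a level only: the power is "calculated with the assumption of liver fat being 4.4-5.0% in this study group at baseline", with no SD. The spread is introduced with "In the power calculation, we have used a coefficient of variation (CV) of" the MRS method, and the text continues "resonance spectroscopy being 11% (17). To detect a 9% difference between study arms with 80% power". The conclusion is that "a minimum sample size of 25 + 25 subjects with a 10% drop-out rate is needed". Section 6 also warns that, because no earlier switch study used MRS "for the quantification of liver fat, the calculation of the study power is an estimate".

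Alpha, sidedness, the primary test and the scale of the 9% are not stated. The tests listed for group comparisons end with "Mann-Whitney U test and others, as appropriate". Section 3 puts the total number of subjects at 45, while section 6 calls 25 + 25 the minimum.

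**The concern.** Power for a between-arm difference in change depends on the between-patient SD of that change. As worded, the 11% describes how precisely MRS measures liver fat. It says nothing about how differently patients' livers respond over 24 weeks, and if it refers to one scan it does not even cover the measurement error of a two-scan difference.

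The 80%/9% statement is the only justification of the sample size for the primary endpoint. It tells the reader that a true 9% difference would be missed one time in five. If the real miss rate is nearer one in two, a non-significant result could be misread as evidence against a 9% effect.

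**Working it through.** **Inputs.** From section 6: difference 9%, CV 11%, power 80%, 25 + 25, drop-out 10%, baseline 4.4-5.0%. From section 3: 1:1 allocation, 45 subjects. Assumed because not stated: two-sided 5% two-sample t-test (noncentral t). The 9% is read as relative, since nine percentage points would be 9/5.0 = 1.8 to 9/4.4 = 2.0 times the assumed baseline. "45 evaluable" means 22.5 per arm.

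**Step 1: reproduce the plan's figure with 11% as the whole SD.**
- Percent scale: difference 9, SD 11 gives 24.4 per arm, so 25 before drop-out (24.4/0.9 = 27.2 after it).
- Log scale: difference |ln 0.91| = 0.0943, SD = sqrt(ln(1 + 0.11²)) = 0.1097 gives 22.2 per arm, and 22.2/0.9 = 24.7 after drop-out.

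Both routes reach 25 per arm, so 11% was probably entered as the SD of the outcome. This is an inference; the rest does not depend on it.

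**Step 2: what the SD of change must contain.** With independent scan errors, SD² of change = 2 × (single-scan error)² + (SD of true change)².

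**Step 3: reading A, 11% is the CV of one scan.** Measurement error alone gives 11 × sqrt(2) = 15.6% (log scale 0.1097 × sqrt(2) = 0.155).

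| Power for 9% | 25 evaluable per arm | 45 evaluable in total |
|---|---|---|
| SD 11%, percent scale | 81% | 76.5% |
| SD 11%, log scale | 85% | 80.5% |
| Two scans, percent scale | 52% | 47.5% |
| Two scans, log scale | 56% | 51% |

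On the two-scan rows, 80% would need 48 (percent) or 44 (log) evaluable per arm, or a single-scan CV of about 7.4-8.3%. A one-sided 5% test on the percent scale would still give only 64% and 60%.

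**Step 4: reading B, 11% is already the measurement SD of the change.** The largest SD compatible with 80% power for 9% is 11.13% (25 per arm) or 10.53% (45 in total) on the percent scale, and 0.1166 or 0.1104 on the log scale. The room left for true variation in response is:
- percent, 25 per arm: sqrt(11.13² − 11²) = 1.7%
- percent, 45 in total: none, since 10.53 < 11
- log, 25 per arm: sqrt(0.1166² − 0.1097²) = 4.0%
- log, 22.5 per arm: sqrt(0.1104² − 0.1097²) = 1.2%

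**Step 5: add some true variation (assumed SD 5% or 10%), 45 evaluable.** Reading B: 68.5% or 51% (percent), 73% or 55% (log). Reading A: 44% or 36% (percent), 48% or 39% (log).

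**Step 6: a rough outside scenario from the plan's own text.** The earlier CAP study is quoted with 19 + 18 subjects and "7,3% decrease in the RAL vs. 11,0% increase in the Efv arm, p = 0,019". The difference is 7.3 + 11.0 = 18.3. A two-sided p of 0.019 on 35 df gives t = 2.459, SE = 18.3/2.459 = 7.44 and SD = 7.44/sqrt(1/19 + 1/18) = 22.6%. This assumes arm means and a t-test, and it comes from another scale, follow-up time and population.

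**Step 7: what the trial can detect with 80% power (percent scale).**

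| SD of change | 45 evaluable | 45 enrolled less 10% (20 per arm) | 95% CI half-width, 45 evaluable |
|---|---|---|---|
| 11% | 9.4% | 10% | 6.6% |
| 15.6% | 13% | 14% | 9.4% |
| 22.6% (from CAP, rough) | 19% | 21% | 13.6% |
| 30% (assumed) | 26% | 27% | 18% |

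**The case against.** The strongest reply is that the 11% comes from a cited source that cannot be consulted here. If that figure were in fact a between-patient SD of change, the claim would be roughly supported: on the log scale power is 85% with 25 evaluable per arm and 80.5% with 45 evaluable. The size of the shortfall therefore depends on the reading, and also on the assumed test, alpha, relative scale and independent scan errors. The reconstruction in step 1 is not unique either: the percent scale reaches 25 only before drop-out, and the documents mention no log transformation. Finally, section 6 itself calls the power an estimate.

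Much of this stands as a limit on how exactly the loss can be stated. It does not restore the claim. The plan labels the 11% as a property of the MRS method, and if it is something else the plan must say so. Even the favourable log-scale figures need near-zero variation in true response, for which the plan offers no basis. The caveat about an estimate concerns the lack of earlier MRS switch studies; it comes with a single figure and no range, and does not say that variation in response was left out.

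**Conclusion.** The concern holds. The arithmetic from 9% and 11% to 25 per arm is sound; the input is the problem. No SD of the 24-week change is given, so 80% power for a 9% difference is not supported on either reading of the 11% as a method CV. On the single-scan reading a true 9% difference would be missed 44-53% of the time, not 20%, before any real variation in response. On the other reading 80% survives only if true change has an SD of at most about 1-4% between patients, and not at all on the percent scale with 45 evaluable.

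These figures rest on a two-sided 5% t-test, a relative 9% and, for the single-scan reading, independent scan errors. The true SD of change cannot be recovered from the documents, so the exact power is unknown.

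The defect lies in the claim and not in the enrolment. For a difference as large as the 18.3% quoted from the CAP study, power with 45 evaluable would be 97% at SD 15.6% and 76% at SD 22.6%, though 52% at SD 30%.

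**What to change.** Replace the last paragraph of section 6:

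- Say that 11% is the CV of the MRS method, and whether it refers to one scan or to a repeat-scan difference.
- Say that no SD of the 24-week change by MRS was available, if that is so, and remove the claim of 80% power for 9%.
- Keep the planned enrolment, but reconcile 45 (section 3) with 25 + 25 (section 6) and say which number is enrolled and which is evaluable. Since 50 less 10% is 45, the latter may be the expected completers, but the text does not say so.
- Give the difference detectable with 80% power over a range of SDs of change, as in step 7, with each SD marked as a scenario and none as a working value.
- State alpha, sidedness, the primary test and whether differences are relative or in percentage points, so that these figures can be checked.
- Say that the primary result will be interpreted from the estimated difference and its 95% confidence interval.

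The cost is one rewritten paragraph and one number aligned with section 3. No extra patients are needed, and the design and endpoint do not change. Naming the test, alpha and scale does add detail that the analysis section now lacks. The drawback is that the stated sensitivity becomes less favourable.
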